Study Protocol **(including Statistical Analysis plan)**

Title

- Does the use of LiDCOplus alter decision-making in fluid prescription during resuscitation in the Intensive Care Unit?
- Or Use of LiDCOplus in Fluid Resuscitation Decision-Making

Introduction

- Rationale

Unwell patients in the intensive care unit (ICU) often need supplementary fluids to be given into the bloodstream through a drip in a vein (venous cannula), however too much fluid can be harmful. It can sometimes be difficult to tell whether or not a patient will benefit from extra fluids so they are given a "fluid challenge", whereby a small volume of fluid is given quickly into the cannula and the change in their status is noted. If the patient's condition improves, this suggests that the patient is "fluid responsive" and needs more fluid.

A LiDCOplus cardiac output monitor is a device used in the ICU to estimate the amount of blood ejected from the heart on each heartbeat using pressure readings obtained from a tube placed in one of the patient's arteries (arterial line).

We aim to determine whether or not the use of this device called makes a difference to the judgement of "fluid responsiveness" when the patient is given a fluid challenge when compared to simply using measurements of pulse and blood pressure and assessing the circulation in the patient's limbs. This will allow us to determine whether or not the LiDCOplus cardiac output monitor alters the decisions made by doctors and nurses about how much fluid to give their patients and hence if it is of any benefit.

- Background information including literature review

In the published literature there are multiple studies using the LiDCOplus-derived change in stroke volume as a gold standard of fluid responsiveness against other measures such as stroke volume variation and pulse pressure variation^{1,2}. However there do not seem to be any studies evaluating the change in stroke volume itself as a measure of fluid responsiveness against clinical parameters, as proposed in the current study.

There are two studies which compare outcomes in patients whose fluid therapy was guided by LiDCO vs controls. One was a pilot study of 21 severely burned adults which compared fluid therapy in patients with and without LiDCO monitoring and showed that the LiDCO group received significantly less fluid³. The other was a study on intra-operative patients undergoing surgical repair of fractured neck of femur under spinal anaesthetic⁴ and is not relevant to the critically unwell patients in the intensive care unit we wish to study.

There does, therefore, appear to be a lack of current evidence to address the research question and further research in to this area would be desirable.

- Potential risk and benefits

The results of this study should benefit patients in ICU by evaluating the usefulness of a piece of equipment used regularly to guide patient care. If it is shown to be useful, this may encourage its use in order to gain maximum benefit for patients. If it is shown not to be useful, this may lead to a reduction in its use and subsequent cost savings to ICU departments which can use the extra money to improve patient care in other areas.

There is minimal potential for direct benefit to patients as the research does not involve any change to their standard monitoring and treatment. However, there may be a benefit in the special attention paid to the patients' response to fluids e.g. minimising errors and picking up additional information from the patient's assessment.

There are minimal potential risks for research participants as their monitoring or treatment will not be affected apart from a very brief delay while the clinician fills out the research proforma by the bedside.

- Prior experience of intervention

The LiDCOplus device is widely used in the authors' intensive care unit to guide fluid therapy in patients requiring fluid resuscitation. It is thought that this allows administered fluid volumes to be tailored to maximize benefit and minimise harm to the patient it is not entirely clear from clinical experience whether or not this is the case.

- Study Hypothesis

The Null Hypothesis is there is no difference to the judgement of "fluid responsiveness" using information from a LiDCOplus monitor when a patient is given a fluid challenge, when compared to simply using standard clinical measurements of responsiveness.

Aim/Primary and Secondary Objectives

- **Primary Endpoint**
To determine whether or not use of the LiDCOplus cardiac output monitor results in an estimate of a patient's response to a fluid challenge which is significantly different to that simply obtained using standard measures of blood pressure, heart rate and limb circulation.
- **Secondary endpoints**
[None]

Methodology

A patient undergoing fluid resuscitation guided by a LiDCOplus device will have a research data pro forma left at their bedside along with instructions on how to complete it. When a patient is given a fluid challenge (the fast intravenous administration of 250ml of Hartmann's solution) as part of their routine management, a number of additional actions will take place. The screen of the LiDCOplus will be covered up initially and baseline heart rate, blood pressure and subjective assessment of limb circulation will be recorded on the proforma. After the fluid challenge is administered the above observations will be recorded again and at this point an assessment of whether the patient is "responsive" or "unresponsive" will be made. The LiDCOplus screen will then be uncovered and the change in stroke volume will be recorded (the cut off for being fluid responsive is a change of >10%). Finally, an overall decision regarding fluid responsiveness is made and recorded, along with the grade of decision maker (e.g. staff nurse or consultant).

This observational study will be performed according to the Research Governance Framework for Health and Community Care (Second edition, 2006).

Study Population

The study population will be a convenience sample as appropriate to the study type so the exact number of participants is not known as yet.

We aim to include all patients undergoing fluid resuscitation using a LiDCOplus cardiac output monitor in Glasgow Royal Infirmary Intensive Care Unit during the study period.

The researchers will regularly review the patients on the ICU to identify suitable participants.

Inclusion criteria

- Adult patients
- Admitted to Intensive Care Unit (ICU)
- Undergoing fluid resuscitation guided by fluid challenges
- Monitored by a LiDCOplus cardiac output monitor attached to an arterial line

Exclusion criteria

- Poor arterial line trace
- Moribund state
- Patient / relative refusal
- Contra-indication to fluid bolus

Identification of participants and consent

All eligible patients as per the inclusion and exclusion criteria will be identified and included in the study, which will simply involve a single-sheet pro forma being placed at their bedside for the clinical staff to complete when the patient undergoes a fluid challenge.

The direct care team will carry out the data gathering by completing the pro forma and the research team (who are part of the clinical team) will also be involved to remind the rest of the clinical team about the study and ensure any questions are answered.

Given that the patients will not experience any difference in their care but the clinical staff will have to perform some extra steps when administering a fluid challenge, it is the clinical staff (nurses and doctors) involved who will be asked for their informed consent to take part in the study.

Study Outcome Measures

4.1 Primary Outcome Measure

Proportion of decisions about fluid management changed by knowledge of the change in stroke volume post fluid challenge, as derived by LiDCO cardiac output monitor.

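### The only outcome is worded as changed fluid-management decisions, but the described data and both planned statistics concern fluid-responsiveness judgements, and the protocol never equates the two

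*Protocol*

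**What the plan says.** The protocol describes its question in two vocabularies.

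**Fluid management or prescription**
- Title: "Does the use of LiDCOplus alter decision-making in fluid prescription during resuscitation in the Intensive Care Unit".
- Section 4.1, the only outcome measure (section 4.2 lists no secondary one): "Proportion of decisions about fluid management changed by knowledge of the change in stroke volume post fluid challenge".
- Introduction, Rationale, which expects the responsiveness comparison to show whether the monitor changes what staff decide "about how much fluid to give their patients and hence if it is of any benefit".

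**Fluid responsiveness**
- Study Hypothesis, where the null is: "no difference to the judgement of 'fluid responsiveness' using information from a LiDCOplus monitor when a patient is given a fluid challenge".
- Primary Endpoint, which concerns an estimate of the patient's "response to a fluid challenge which is significantly different to that simply obtained using standard measures".
- Methodology: a responsive/unresponsive assessment is made with the monitor screen covered. The screen is then uncovered, the stroke volume change is recorded, and "an overall decision regarding fluid responsiveness is made and recorded".
- Statistics and Data Analysis: two descriptive statistics. One compares the proportion of patients judged responsive with LiDCOplus and with standard parameters alone. The other is the proportion of responsiveness decisions altered once the LiDCOplus information is considered.

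The Rationale offers a partial bridge between the two. It says that improvement after a challenge suggests a patient who is fluid responsive and who needs more fluid.

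**The concern.** A sole primary outcome should be the quantity that the data collection and the analysis produce. Here the outcome carries a broader label than anything the protocol says will be recorded or summarised. The figure the study will produce is the rate of altered responsiveness judgements. Under the wording of section 4.1 and the title, a reader would take it as the rate at which the monitor changes fluid management.

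The difference matters because of the use intended for the result. The Rationale means to go from the comparison to the quantity of fluid given, and from there to benefit. The Potential risk and benefits section adds, conditionally: "If it is shown not to be useful, this may lead to a reduction in its use". A changed opinion about responsiveness is a weaker basis for that step than a changed fluid decision.

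**Working it through.** The protocol states no sample size, rate or effect size, so there is no figure to reproduce. The check is a count of what is recorded and analysed, followed by what that permits.

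**1. Data items described in the Methodology**
- Heart rate, blood pressure and limb circulation, before and after the challenge: 3 × 2 = 6
- Responsiveness assessment with the screen covered: 1
- Change in stroke volume: 1
- Overall responsiveness decision after uncovering: 1
- Grade of decision maker: 1
- Total: 6 + 1 + 1 + 1 + 1 = 10

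Responsiveness judgements: 2 of 10. Decisions to give, withhold or size further fluid: 0 of 10.

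**2. Statistics named in Statistics and Data Analysis**

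On responsiveness: 2 of 2. On fluid management: 0 of 2.

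**3. Place by place**

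| Place in protocol | Fluid management | Fluid responsiveness |
|---|---|---|
| Title | yes | no |
| Rationale | yes (intended inference) | yes (the comparison) |
| Study Hypothesis | no | yes |
| Primary Endpoint | no | yes |
| Methodology, recorded judgements | no | yes |
| Section 4.1 | yes | no |
| Planned statistics | no | yes |

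**4. What the described data can identify**

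Let *J* be the proportion of challenges in which the responsiveness judgement changes on uncovering, and *M* the proportion in which the fluid decision changes. Let *a* be the proportion in which the judgement changes but the fluid decision does not, and *b* the proportion in which the fluid decision changes but the judgement does not. Then

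*M* = *J* − *a* + *b*.

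The described items give *J*. They give neither *a* nor *b*, so *M* equals *J* only on the unverified assumption that *a* = *b* (both zero if the two constructs are the same thing).

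Two statements in the Rationale show why that assumption is not automatic. It warns that excess fluid can do harm, so a fluid decision may weigh more than responsiveness. It also speaks of the quantity of fluid, on which a two-category judgement carries no information.

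**The case against.** The best defence is that section 4.1 is loose wording for the second planned statistic. The parallel is close. Both are proportions of decisions, both turn on what the monitor adds, and both fit the sequence of judging with the screen covered, uncovering and judging again. There is one outcome and no secondary outcome, so no rival quantity competes for the label. The Rationale treats a responsive patient as one who needs more fluid and says outright that the comparison will inform decisions on quantity. Six of the ten items are bedside observations that bear on neither side, so the count shows only that no fluid-decision item is described. The pro forma is not shown and might contain one.

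Much of this stands. A reader might infer that the analysis is undetermined, or that the protocol offers no link between the two constructs. Neither is supported: what will be calculated is clear, and the link is stated. A reader might also infer that the link could never be checked. That goes too far while the pro forma is unseen; the limit is to the data items described.

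What remains is that the link is given as a suggestion and an expectation, not a definition, and section 4.1 does not adopt it. Because the title also asks about prescription, section 4.1 cannot be dismissed as a slip. Even if the pro forma does hold a fluid plan, neither named statistic uses it.

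**Conclusion.** The point holds as a mismatch between the sole outcome as worded and the hypothesis, endpoint, described data and planned statistics. It should be fixed, but it does not undermine the calculation itself. As worded, the section 4.1 proportion cannot be computed from the described data; the nearest computable quantity is the proportion of responsiveness decisions altered.

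The size can be given only as counts: 0 of 10 described items and 0 of 2 named statistics concern a fluid decision. Without expected proportions, neither the size nor the direction of the gap between changed judgements and changed fluid decisions can be stated.

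A reader might conclude that the protocol already claims benefit or lack of it. It does not: the Rationale states an intended inference, and the sentence on reduced use is conditional and not tied to section 4.1. The fair criticism is that the intended inference goes further than the described data can support.

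The verdict assumes that the Methodology describes the recorded judgements in full. If the pro forma also records a fluid plan, the data gap closes, but the gap in the analysis does not.

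**What to change.** **Preferred: align the outcome with the data.** Redefine section 4.1 as the proportion of fluid-responsiveness judgements that change between the assessment made before the screen is uncovered and the overall decision made after it. Limit the title, and the Rationale's statements on quantity of fluid and on benefit, to responsiveness judgements. This is rewording in those places only, with no new data. The cost is that the study no longer claims to answer a question about fluid prescription.

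**Alternative, if the prescription question is to be kept.** Add one record-only item to the single-sheet pro forma, *further fluid intended: yes / no*, answered before and again after uncovering. Report the proportion of challenges in which the answer changes as the section 4.1 outcome, alongside the proportion of responsiveness judgements changed. Carry the item into the Study Hypothesis, Primary Endpoint, Methodology, and Statistics and Data Analysis. The title can then stand, but the Rationale should speak of whether further fluid is intended, not of its quantity, and should drop the inference to benefit. The cost is a few seconds per challenge, and the item captures intention, not volume.

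Neither option changes patient care. Either needs the amendment and approvals set out under Protocol Amendments.

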4.2. Secondary Outcome Measure

None

Statistics and Data Analysis

As this is a descriptive study only descriptive statistics will be used, i.e. the proportion of patients deemed fluid-responsive by the use of LiDCOplus versus standard parameters alone and the proportion of fluid responsiveness decisions altered when the information from the LiDCOplus is taken into account.

STUDY CLOSURE / DEFINITION OF END OF TRIAL

The study will end when the planned sample size has been achieved.

Protocol Amendments

Any change in the study protocol will require an amendment. Any proposed protocol amendments will be initiated by the CI following discussion with the TSC and any required amendment forms will be submitted to the regulatory authority, ethics committee and sponsor. The CI and the TSC will liaise with study sponsor to determine whether an amendment is non-substantial or substantial. All amended versions of the protocol will be signed by the CI and Sponsor representative. Before the amended protocol can be implemented favourable opinion/approval must be sought from the original reviewing REC and Research and Development (R&D) office(s).

Ethics

The study will be carried out in accordance with the World Medical Association Declaration of Helsinki (1964) and its revisions (Tokyo [1975], Venice [1983], Hong Kong [1989], South Africa [1996] and Edinburgh[2000]).

Favourable ethical opinion will be sought from an appropriate REC before patients are entered into this study.

The CI will be responsible for updating the Ethics committee of any new information related to the study.

Finance and Indemnity

NHS employed researchers will be covered for negligent harm through the NHS CNORIS indemnity scheme. If you are a University employee you may need extra cover for non-negligent harm through your University. Please check this with your Research and Enterprise department.

The study is sponsored by NHS Greater Glasgow & Clyde. The sponsor will be liable for negligent harm caused by the design of the trial. NHS indemnity is provided under the Clinical Negligence and Other Risks Indemnity Scheme (CNORIS).

Publications

Study results whether, negative or positive, should be disseminated. Details of your plan for dissemination should be included here.

Reference

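### The protocol poses a null hypothesis and a significance-worded primary endpoint, but its analysis is limited to two descriptive proportions with no interval or test

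*Protocol*

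**What the plan says.** The title line of the protocol says that the document contains the statistical analysis plan. The relevant statements are these.

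- **Study Hypothesis:** "The Null Hypothesis is there is no difference to the judgement of" fluid responsiveness, with the monitor's information compared with standard clinical measurements.
- **Primary Endpoint:** whether the monitor yields an estimate of response "which is significantly different to that simply obtained using standard measures of blood pressure, heart rate and limb circulation".
- **Methodology:** three items are recorded at each challenge. The first is a responsive/unresponsive call with the screen covered. The second is the change in stroke volume once the screen is uncovered, where "the cut off for being fluid responsive is a change of >10" per cent. The third is the clinician's conclusion: "Finally, an overall decision regarding fluid responsiveness is made and recorded".
- **4.1 Primary Outcome Measure:** "Proportion of decisions about fluid management changed by knowledge of the change in stroke volume post fluid challenge".
- **Statistics and Data Analysis:** "As this is a descriptive study only descriptive statistics will be used". The section names two quantities. One is "the proportion of patients deemed fluid-responsive by the use of LiDCOplus versus standard parameters alone". The other, which corresponds to the primary outcome in 4.1, is "the proportion of fluid responsiveness decisions altered when the information from the LiDCOplus is taken into account".
- **Study Population and Study Closure:** the sample is one of convenience and its number is not yet known, yet the study is to stop at a planned size that is not given.

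**The concern.** A null hypothesis and the word significantly both promise an inferential answer. The analysis section does more than omit one: it confines the analysis to description and gives what reads as a closed list of two proportions. Followed as written, the study would report a bare percentage of decisions altered, beside an aim that this percentage cannot settle. The protocol says that its result may encourage use of the device or reduce it to save money, so a reader needs to know how firmly the percentage is estimated. With an unspecified convenience sample, precision could be poor.

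There is a smaller fault in the list itself. The first proportion does not say which of the two recorded items it counts as the monitor's verdict, and it counts patients while the second counts decisions. The outcome in 4.1 also refers to fluid management, whereas the pro forma items and the analysis concern judgements of fluid responsiveness.

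**Working it through.** The protocol gives no sample size, significance level, power or expected proportion, so there is no figure of its own to reproduce. The check is a comparison of the text, followed by illustrations in which every count is an assumption.

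**1. Question against analysis.** The Study Hypothesis and the Primary Endpoint ask whether two judgements differ, the second using the word significantly. Statistics and Data Analysis offers two proportions, with no interval, test or decision rule. Nothing in the listed analysis bears on a statement of significance.

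**2. Which quantities are clear.** The second listed proportion compares the covered-screen call with the final overall decision. It matches the 4.1 outcome and the Methodology, so the primary quantity is defined. The first listed proportion could take either the final decision or the stroke-volume result above 10% as the monitor's verdict. These can differ within one challenge.

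**3. Unstated precision.** Assume that 25% of decisions are altered and that each patient contributes one challenge. The exact (Clopper-Pearson) 95% limits for x of n are the 0.025 quantile of Beta(x, n−x+1) and the 0.975 quantile of Beta(x+1, n−x).

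| Altered / challenges | 95% interval |
|---|---|
| 5/20 | 8.7% to 49.1% |
| 10/40 | 12.7% to 41.2% |
| 25/100 | 16.9% to 34.7% |

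**4. What a paired test would address.** Assume that 10 of 50 decisions change. The exact two-sided paired (McNemar) test uses only the split of those 10 between changes to responsive and changes to unresponsive. The p-values are 1.00 for a 5/5 split, 0.11 for 8/2, 0.021 for 9/1 and 0.002 for 10/0. The same 20% altered can therefore go with no net shift or a clear one. Such a test concerns net shift in the proportion judged responsive, which is not the primary proportion.

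**5. Direction of change.** Assume 100 challenges, 50 responsive on the covered call, 60 responsive by the monitor and 30 decisions altered. Let b be changes to responsive and c changes to unresponsive, so b + c = 30.

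- *If the 60 are final decisions:* b − c = 60 − 50 = 10, so b = 20 and c = 10. The direction is recovered, provided both proportions use the same unit.
- *If the 60 are stroke-volume results:* b − c is not reported. With no restriction on how decisions change, b could be anything from 0 to 30, and the final number responsive, 50 + b − c, anything from 20 to 80.

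Now suppose that decisions move only towards the stroke-volume result, and let x challenges be positive on both the covered call and stroke volume. Both are negative in 100 − 50 − 60 + x = x − 10, so the two agree in x + (x − 10) = 2x − 10 challenges. Also b ≤ 60 − x and c ≤ 50 − x.

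| x | Agreement per 100 | Possible b | Final responsive |
|---|---|---|---|
| 20 | 30 | 0 to 30 | 20 to 80 |
| 30 | 50 | 10 to 30 | 40 to 80 |
| 40 | 70 | 20 only | 60 |

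Agreement by chance would be 0.5 × 0.6 + 0.5 × 0.4 = 50%. Under this condition the full 0-to-30 range needs agreement of 30% or less. At 70% agreement the split is the same as under the final-decision reading.

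**The case against.** The strongest reply is that the working part of the plan is coherent. Both calls are recorded, the primary outcome is the proportion changed, and the analysis reports that proportion. A descriptive design is legitimate for an observational study. The protocol never says statistically significant and sets no significance level or power, so significantly may be meant loosely. If counts are published, a reader can compute an exact interval, at least with one challenge per patient.

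Much of this stands. A reader might infer that a descriptive analysis is the wrong choice, or that a hypothesis test is required. The documents support neither, because the design can be answered by estimation. A reader might also infer that the primary outcome is undefined, and it is not. On the first listed proportion, the contrast with standard parameters alone and the choice of the verb deemed both lean towards the clinician's final decision. The gap between fluid management and fluid responsiveness is also partly bridged by the Rationale, which says that a responsive patient needs more fluid.

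What does not stand is the suggestion that nothing needs correcting. Even with significantly read loosely, a formally stated null hypothesis is left with no analysis. Deferral to a separate plan is a weak defence, since the title line says this document includes the plan and its wording excludes inference rather than leaving it open. An interval that readers must derive for themselves is not a planned analysis, and they could not derive it if patients contribute several challenges.

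**Conclusion.** The point holds as an inconsistency between the stated question and the planned analysis, together with unstated precision for the primary proportion. It is worth fixing before the analysis is carried out, but it is not a numerical error and does not invalidate the design. On assumed figures (25% altered, independent challenges), the unreported uncertainty would be 9% to 49% with 20 challenges and 17% to 35% with 100.

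The ambiguity over the monitor's verdict is secondary and confined to the first listed proportion. A reader might infer that the report would leave the direction of change wholly unknown, anywhere from 0 to 30 upward changes in the worked example. That is the worst case only. It requires the less natural reading and, if decisions move only towards the stroke-volume result, agreement of at most 30% between the covered call and stroke volume. Confidence is high on the mismatch in wording and lower on how far direction would be lost in practice.

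**What to change.** 1. **Study Hypothesis and Primary Endpoint:** reword as an estimation aim, dropping the null hypothesis and the word significantly. If the sponsor prefers to keep a hypothesis, pre-specify a paired test and label it as a test of net shift in the proportion judged responsive.
2. **4.1 Primary Outcome Measure:** replace the reference to fluid management with the fluid responsiveness decisions that are actually recorded.
3. **Statistics and Data Analysis, primary quantity:** report the proportion of challenges whose final overall decision differs from the covered-screen call, with a 95% confidence interval. Use an exact interval if each patient contributes one challenge. Use one that allows for clustering by patient if any contributes more, which the protocol does not exclude.
4. **Same section, direction:** report the paired two-by-two table of covered-screen call by final decision.
5. **Same section, definition:** state that a verdict reached with the monitor means the final overall decision, use one counting unit throughout, and report any comparison with the 10% stroke-volume cut-off separately under its own label.

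The cost is wording in four sections and a little extra analysis. Both calls are already recorded. A patient identifier on each sheet is needed if repeat challenges are included and it is not already there (the pro forma is not shown). The price is a less strongly worded aim.

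### Does reporting responsiveness as a proportion of patients leave the summary undefined, given that it is judged at a fluid challenge?

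*Protocol*

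**What the plan says.** The Statistics and Data Analysis section limits the study to descriptive statistics and names two summaries in one sentence. The first is "the proportion of patients deemed fluid-responsive by the use of LiDCOplus versus standard parameters alone". The second is "the proportion of fluid responsiveness decisions altered when the information from the LiDCOplus is taken into account". So the sentence starts with patients and ends with decisions.

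Section 4.1, Primary Outcome Measure, counts decisions: "Proportion of decisions about fluid management changed by knowledge of the change in stroke volume post fluid challenge". Section 4.2 lists no secondary outcome.

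The Methodology section describes one cycle. Observations are taken before and after a 250 ml challenge with the monitor screen covered, and a clinical judgement is made on whether the patient is responsive. The screen is then uncovered and the stroke volume change read against a 10% cut-off. The cycle closes as follows: "Finally, an overall decision regarding fluid responsiveness is made and recorded".

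Two places bear on how many challenges are recorded per patient. The inclusion criteria use a plural: "Undergoing fluid resuscitation guided by fluid challenges". The section on identification of participants and consent uses a singular: "a single-sheet pro forma being placed at their bedside for the clinical staff to complete when the patient undergoes a fluid challenge". No text says first challenge only, and none says every challenge.

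**The concern.** A proportion needs a unit. If responsiveness belongs to a challenge and a patient may contribute several, a proportion of patients needs a rule that turns several results into one status: ever responsive, responsive at the first challenge, or always responsive. The protocol states none, so the rule could be picked after the data are seen. The LiDCOplus versus standard-parameters comparison, which sits close to the study hypothesis, would then depend on that choice.

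There is a second strand. Repeated decisions on one patient are correlated, so a patient with many challenges weighs more in a per-decision proportion, and an interval or test that treats decisions as independent would be too narrow. The Primary Endpoint text invites such a test, since it asks for an estimate "which is significantly different to that simply obtained using standard measures of blood pressure, heart rate and limb circulation".

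The point cannot be set aside as a matter for a later analysis plan, because the document's title says that it includes the analysis plan.

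**Working it through.** The protocol gives no sample size, expected proportion, significance level or number of challenges per patient, so there is no stated figure to reproduce. Every input below is an assumption.

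**1. How far the patient proportion can move.** Let p be the probability that a challenge is judged responsive, ρ the within-patient correlation, and two challenges be recorded per patient (beta-binomial model).

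- Always responsive: p² + ρp(1 − p)
- Ever responsive: 1 − [(1 − p)² + ρp(1 − p)]
- Mixed results: 2p(1 − p)(1 − ρ), which equals ever minus always
- First challenge: p

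With p = 0.40, p(1 − p) = 0.24:

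| ρ | Always | First | Ever | Mixed |
|---|---|---|---|---|
| 0.1 | 0.16 + 0.024 = 0.184 | 0.40 | 1 − 0.384 = 0.616 | 0.48 × 0.9 = 0.432 |
| 0.2 | 0.16 + 0.048 = 0.208 | 0.40 | 1 − 0.408 = 0.592 | 0.48 × 0.8 = 0.384 |
| 0.3 | 0.16 + 0.072 = 0.232 | 0.40 | 1 − 0.432 = 0.568 | 0.48 × 0.7 = 0.336 |

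With three challenges each, ever is 66% to 74% and always 9% to 16% over the same correlations. With independent challenges and two each, the always-to-ever range is 9% to 51% for p = 0.3, 25% to 75% for p = 0.5, and 49% to 91% for p = 0.7.

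**2. Where the spread disappears.** With one recorded challenge per patient, all rules return p. With repeats, the first-challenge rule and a simple count per challenge share the same expected value, p, provided that the response probability does not change from challenge to challenge or depend on how many a patient receives. Only the ever and always rules depart from it, and the protocol mentions neither.

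**3. Which reading the text supports.** Set side by side:

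- Methodology and the consent section: one form, one challenge, one final decision, all singular.
- Methodology: the judgement at a single challenge is already phrased as a property of the patient.
- Inclusion criteria: the plural describes the kind of resuscitation that makes someone eligible. It does not say how many challenges are written down.
- Section 4.1 and the second half of the analysis sentence: decisions.

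Patients in the first half of the sentence therefore reads most naturally as the Methodology's own shorthand for judgements at a challenge.

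**4. The clustering strand.** Simulated coverage of a nominal 95% exact interval that ignores clustering (20 patients, true proportion 25%, 100,000 runs):

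| Challenges per patient | ρ = 0.1 | ρ = 0.2 |
|---|---|---|
| 1 | 96% | 96% |
| 1 or 2 | 97% | 96% |
| 1 to 3 | 96% | 94% |
| drawn from 1, 2, 3, 6, 8 | 91% | 87% |

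Loss is visible only when some patients contribute many challenges, and only for an interval that the protocol does not plan.

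**The case for a change.** The best case for a change is that the text does not settle the matter. The description single-sheet fits the length of the form as well as the number of forms. The Rationale says that a patient who improves needs more fluid, so repeat challenges are to be expected, and bedside staff could follow the present wording either way. The descriptive proportions are the whole planned analysis, so an unclear unit in one of them is not negligible. A clarifying phrase would cost almost nothing, and links between records of the same patient may be hard to recover if not kept at collection.

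Much of this stands. The two units in one sentence are real, and no text restricts recording to one challenge. Three things limit it. Even with repeats, only patients whose results disagree lack a status. The affected item accompanies the primary outcome, and the primary proportion is the same number whichever rule is used. Whether records carry a patient code depends on the pro forma, which is not shown, so its absence cannot be presumed.

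The clustering argument stands less well. It measures the coverage of an interval that the plan excludes by confining itself to descriptive statistics. The tension between that restriction and the hypothesis-testing language of the Study Hypothesis and Primary Endpoint is a separate question and lends no weight here. That patients with more challenges count for more is what any per-decision proportion does.

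**Conclusion.** The mismatch is loose wording in one descriptive summary and calls for no change to the plan. An analyst would count judgements per recorded challenge, in line with the rest of the sentence and with section 4.1, and would give the numbers of patients and challenges beside the result. If one challenge per patient was recorded, patients and decisions coincide and nothing needs interpreting.

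The possible spread is wide only under rules that the protocol never suggests: for example 18% to 23% (always) against 57% to 62% (ever) around a per-challenge 40%, with two challenges each and correlations of 0.1 to 0.3. Those figures rest wholly on assumed inputs. The primary result, the proportion of decisions changed, is unaffected under every reading. This conclusion rests on the singular recording instructions and on the plan remaining descriptive. If an interval or test were added and repeats had been recorded, the patient would have to be treated as the cluster.
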